In addition, aqueous cells and flare, corneal edema, raised IOP and superficial punctate keratitis are examples of early postoperative findings that are typically observed following ocular surgery. These are not considered AEs if they are not severe in nature or can reasonably be expected to resolve within a month and not result in any untoward long term visual outcome impact. The Investigator must assess and determine whether an AE has occurred.

All ocular AEs for the study eye and the contralateral non-study eye, as well as non-ocular AEs, must be reported as part of this study.

For each recorded event, the ADEs and SAEs documentation must include: date of occurrence, severity, treatment (if applicable), outcome, and assessments of the seriousness and causality. In addition, the Investigator must document all device deficiencies reported or observed with test and control articles on the Device Deficiency eCRF. The site must submit all available information on ADEs, SAEs, and device deficiencies to the Study Sponsor immediately as follows:

- ≠ All SAEs must be reported immediately (within 24 hours) of the Investigator's or site's awareness.
- ≠ ADEs that do not meet seriousness criteria and device deficiencies must be reported within 10 calendar days of the Investigator's or site's awareness.

A printed copy of the completed *Serious Adverse Event and Adverse Device Effect* and/or *Device Deficiency* eCRF must be included with product returns.

- ≠ Additional relevant information after initial reporting must be entered into the eCRF as soon as the data become available.
- ≠ Document any changes to concomitant medications on the appropriate eCRFs.
- ≠ Document all relevant information from Discharge Summary, Autopsy Report, Certificate of Death etc., if applicable, in narrative section of the *Serious Adverse Event and Adverse Device Effect* eCRF.

Note: Should the EDC system become non-operational, the site must complete the appropriate paper *Serious Adverse Event and Adverse Device Effect* and/or *Device Deficiency* Form. The completed form is faxed or emailed to the Study Sponsor at [name] according to the timelines outlined above; however, the reported information must be entered into the EDC system once it becomes operational.

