6.3 Secondary Safety Endpoints

All secondary safety endpoints will be evaluated at 36 months postoperatively.

≠ Rate of occurrence of sight-threatening adverse events including,

- Persistent (at time of study exit) BCDVA loss of 3 or more lines compared to best BCDVA achieved during the course of study
- Endophthalmitis
- Corneal decompensation
- Retinal detachment
- Severe choroidal hemorrhage or detachment
- Aqueous misdirection

$$Rate = \frac{\# \text{ of subjects who experience any sight - threatening adverse events}}{\# \text{ of subjects in ITT set}}$$

≠ Rate of ocular secondary surgical interventions (SSI)

$$Rate = \frac{\# \text{ of subjects with any ocular SSIs}}{\# \text{ of subjects in ITT set}}$$

≠ Rate of ocular SSIs associated with CyPass placement and stability

$$Rate = \frac{\# \text{ of subjects with any ocular SSIs associated with CyPass placement and stability}}{\# \text{ of subjects in ITT set}}$$

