6.4 Other Safety Outcomes

The following safety outcomes will be summarized by numerator (number of eyes experiencing the outcome), denominator (number of eyes in the ITT set), and the rate of ITT eyes experiencing the outcome.

≠ Increase from baseline IOP of 10 mmHg or greater at any time at/after 30 days postoperative

- Change in IOP from baseline at/after 30 days postoperative is defined as,

$$Change = PostOp IOP - Baseline IOP$$

- Note: for subjects having IOP change ≥ 10 mmHg at any time at/after 30 days postoperative, a subject will be counted only once for reporting this outcome across all postoperative visits..

- # BCDVA loss of 2 or more lines compared to screening (Visit 0)
 - Change in BCDVA from screening to any postoperative visit is defined as,

$$Change = PostOp BCDVA - Screening BCDVA$$

- # BCDVA loss of 2 or more lines in comparison with best recorded BCDVA at any postoperative visit.

Note: for subjects with BCDVA loss of 2 or more lines to any visit, a subject will be counted only once for reporting this worsening across all postoperative assessments.

- # Device movement, defined as a change by at least 1 in the number of CyPass rings visible (e.g., from 1 ring to 2 rings or from 3 rings to 2 rings) that does not result in clinical sequelae (e.g., secondary surgical intervention to modify device position, corneal endothelial touch by device, corneal edema leading to loss of BCDVA > 2 lines at the last postoperative visit in comparison with preoperative BCDVA, progressive endothelial cell loss, erosion of device through sclera, or device obstruction requiring secondary surgical intervention), and that is not attributable to any one or more of the following:
 - o variations in gonioscopic viewing angle or illumination
 - o changes in angle anatomy due to concomitant findings such as resolution of hyphema
 - o changes in anterior chamber depth
 - o development of focal peripheral anterior synechiae

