6.5 Additional Safety Assessments

6.5.1 Adverse Events

The applicable definition of an Adverse Event (AE) can be found in the study protocol Section 13 Device Deficiencies and Adverse Events. All AEs occurring from when a subject signs informed consent to when a subject exits the study will be accounted for in the reporting. Timing of the adverse event is specified by the investigator on the case report

form when the “Description of Adverse Event” category is selected. *Systemic* adverse events include non-ocular events and events in the fellow eye.

An overall summary of treatment emergent adverse events will be provided including the number and percentage of unique subjects/eyes with at least one AE, AE in the study eye, serious AE in the study eye, systemic AE, serious systemic AE, device related AE (ADE), serious device related AE (SADE), and AE leading to withdrawal.

Descriptive summaries (subject counts and percentages, event counts) for AEs will be presented by primary SOC and PT of the Medical Dictionary for Regulatory Activities (MedDRA) dictionary (Version 19.0 or a more recent version). The SOCs will be presented in alphabetical order. PTs will be ordered in decreasing proportion. The following summary tables and corresponding subject listings will be provided:

- ≠ Non-serious AEs in the study eye (TEAE only)
- ≠ Serious AEs in the study eye (TEAE only)
- ≠ Non-serious systemic AEs for all enrolled subjects (includes non-ocular events and events in the fellow eye)
- ≠ Serious systemic AEs for all enrolled subjects (includes non-ocular events and events in the fellow eye)
- ≠ Adverse device effects (ADE) for all study eyes(TEAE only)
- ≠ Serious adverse device effects (SADE) for all study (TEAE only)
- ≠ All adverse events occurring in the study eye prior to surgery

Both subject and event counts will be presented for AEs. Subject counts refer to the number of subjects with the respective AE of interest. Subjects who experience multiple AEs for a PT will be counted once, similarly for subjects with multiple AEs per SOC, for subject counts. Event counts refer to the number of occurrences of the respective AE of interest, regardless of whether a subject already had this event.

Additionally, individual subject listings provided will include:

- ≠ Deaths for all enrolled subjects
- ≠ Withdrawals due to AE(s) for all enrolled subjects

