
There is a clinical sequela resulting from device position including, but not limited to:
 
Secondary surgical intervention to modify device position (eg, repositioning, proximal end trimming or explantation)
 
Corneal endothelial touch by device
 
Corneal edema leading to loss of BCDVA > 2 lines at the last postoperative visit, in comparison with preoperative BCDVA
 
Progressive ECL, defined as ongoing reduction in endothelial cell count of 30% or more relative to the screening ECD value, where 'ongoing reduction in endothelial cell count' is defined as losses continuing after Visit 5 (6 Month Follow-up)
 
Erosion of device through sclera
 
Device obstruction requiring secondary surgical intervention.
		Postop - cc) CyPass device malposition - positioning after deployment such that there is a clinical sequela resulting from device position (as defined in the protocol) (Specify)
Secondary Safety Endpoints		
Rate of occurrence of sight-threatening adverse events including		

Endpoint	CRF	Comments
Persistent (at time of study exit) BCDVA loss of 3 or more lines compared to best BCDVA achieved during the course of study	Adverse Event(s) SX	Postop - b) Persistent BCDVA loss of 3 lines or more (as defined in the protocol)
Endophthalmitis	Adverse Event(s) SX	Postop - d) Endophthalmitis
Corneal decompensation	Adverse Event(s) SX	Postop - n) Corneal decompensation
Retinal detachment	Adverse Event(s) SX	Postop - p) Retinal detachment
Severe choroidal hemorrhage or detachment	Adverse Event(s) SX	Postop - t) Choroidal hemorrhage or choroidal effusion (as defined in the protocol) lasting longer than 1 month (Specify)
Aqueous misdirection	Adverse Event(s) SX	Postop - h) Aqueous misdirection
The rate of ocular secondary surgical interventions (SSI)	Adverse Event(s) SX	
Any one of these four:
 
Postop - ee) CyPass device explantation associated with CyPass placement and stability
 
Postop - ff) CyPass device explantation NOT associated with CyPass placement and stability
 
Postop - gg) Unplanned ocular surgical reintervention associated with CyPass placement and stability
 
Postop - hh) Unplanned ocular surgical reintervention NOT associated with CyPass placement and stability (as defined in the protocol)

Endpoint	CRF	Comments

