The rate of ocular SSIs associated with CyPass placement and stability	Adverse Event(s) SX	
Either of these two:
 
Postop - ee) CyPass device explantation associated with CyPass placement and stability
 
Postop - gg) Unplanned ocular surgical reintervention associated with CyPass placement and stability

Other Safety Endpoints		
Increase from baseline IOP of 10 mmHg or greater at any time at/after 30 days postoperative	Baseline: Intraocular Pressure_Glaucoma PostOp: Intraocular Pressure_Glaucoma_1	
BCDVA loss of 2 or more lines compared to screening (Visit 0)	Baseline: Visual Acuity_VAS PostOp: Visual Acuity_VAS_1	
BCDVA loss of 2 or more lines in comparison with best recorded BCDVA at any postoperative visit	Baseline: Visual Acuity_VAS PostOp: Visual Acuity_VAS_1	

Endpoint	CRF	Comments
Device movement, defined as a change by at least 1 in the number of CyPass rings visible (eg, from 1 ring to 2 rings or from 3 rings to 2 rings) that does not result in clinical sequelae (eg, secondary surgical intervention to modify device position, corneal endothelial touch by device, corneal edema leading to loss of BCDVA > 2 lines at the last postoperative visit in comparison with preoperative BCDVA, progressive endothelial cell loss, erosion of device through sclera, or device obstruction requiring secondary surgical intervention), and that is not attributable to any one or more of the following:	Adverse Event(s) SX	Postop - dd) CyPass device dislodgement or movement, without sequelae (as defined in the protocol)
variations in gonioscopic viewing angle or illumination		
changes in angle anatomy due to concomitant findings such as resolution of hyphema		
changes in anterior chamber depth		
development of focal peripheral anterior synechiae		

Endpoint	CRF	Comments
Additional Safety Assessments		
Adverse events (ocular and non-ocular)	Adverse Event(s) SX	
Device deficiencies	Device Deficiency	
Endothelial Cell Count	This will come from a dataset provided by the reading center, CIARC	
Slit lamp findings	Baseline: Slit Lamp Observations PostOp: Slit Lamp Observations_1	
Fundus examination (C/D ratio) and fundus findings	Baseline C/D: Fundus Exam PostOp C/D: Fundus Exam_1 Baseline observations: Fundus Observations PostOp observations: Fundus Observations_1	
Corneal pachymetry	Baseline: Corneal Thickness PostOp: Corneal Thickness_1	
Intraocular pressure	Baseline: Intraocular Pressure_Glaucoma PostOp: Intraocular Pressure_Glaucoma_1	

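### Persistent 3-line vision loss in the sight-threatening rate should be derived from the acuity data already collected, not taken only from adverse event item b)

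*SAP*

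**What the plan says.** SAP 6.3 lists, as the first component of the sight-threatening rate, "Persistent (at time of study exit) BCDVA loss of 3 or more lines compared to best BCDVA achieved during the course of study". The numerator is the number "of subjects who experience any sight - threatening adverse events" and the denominator is the ITT set. SAP 6.3.1 attaches no hypothesis to it.

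SAP Appendix C names the data source for each endpoint. For this component it names only the form Adverse Event(s) SX, with the entry "Postop - b) Persistent BCDVA loss of 3 lines or more (as defined in the protocol". For the outcome "BCDVA loss of 2 or more lines in comparison with best recorded BCDVA at any postoperative visit", and for the 2-line loss against screening, it names "Baseline: Visual Acuity_VAS PostOp: Visual Acuity_VAS_1" and no adverse event form. SAP 6.4 also gives a formula for the loss against screening, introduced by "Change in BCDVA from screening to any postoperative visit is defined as".

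Protocol 13.1.2 lists the 3-line loss as postoperative event b). Protocol 13.1.3 pre-defines it as sight threatening and requires it to be reported as an SAE.

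**The concern.** The component is a comparison of numbers recorded at scheduled visits, but the plan never computes it. An eye enters the rate through this component only if someone at the site notices that exit acuity is three lines below the best earlier reading and enters item b). The milder 2-line loss needs no such step. If the entry is missed, an eye that meets the written definition is left out of the sight-threatening rate, although its acuity values are in the database. At stake is the completeness of a secondary safety rate in a post-approval safety study, where few events of each type may be expected and a single missed eye would be visible in the result.

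**Working it through.** **1. Endpoint type against data source (SAP Appendix C, with Protocol 13.1.2 and 13.1.3)**

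| Outcome | Set by measured values? | Also a protocol-listed AE? | Source in Appendix C |
|---|---|---|---|
| 3-line loss at exit against best | Yes | Yes, item b), mandatory SAE | AE form only |
| 2-line loss against screening | Yes | Not with this reference | Visual Acuity forms |
| 2-line loss against best recorded | Yes | Only as part of item y), hypotony | Visual Acuity forms |
| IOP rise of 10 mmHg or more | Yes | Yes, closely matching item z) | IOP forms |
| Other five sight-threatening components | No, clinical diagnoses | Yes | AE form |

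The IOP row shows that being a listed AE does not, in this SAP, rule out derivation from measurements.

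**2. Are the data there?** The visit schedule has BCDVA at every postoperative visit (pinhole at Visit 1), including Visit 8. Protocol 12.4 asks for Visit 8 procedures at early exit where the subject can be brought back.

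**3. The threshold in letters.** Protocol 13.1.2 item a) equates 2 lines with 10 letters, so one line is 10 / 2 = 5 letters. SAP Appendix E agrees: 5 letters per 0.1 logMAR. Three lines are 3 × 5 = 15 letters.

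**4. Could a site overlook it?** Take a hypothetical cataract eye with screening 75 letters, best 98 and exit 82. Loss from best is 98 − 82 = 16 letters, which meets the rule. Change from screening is 82 − 75 = +7 letters, so a comparison with baseline shows a gain. The protocol also uses other acuity references for other events: Visit 3 for item a), best postoperative for part of item y), and preoperative for part of item cc).

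**5. Does any stated step add an unreported eye to the rate?**
- Protocol 13.1.3 makes SAE reporting mandatory, but the loss must first be recognised. Protocol 13.3, in its paragraph on early postoperative findings, says "The Investigator must assess and determine whether an AE has occurred".
- Protocol 13.3.1 lets the sponsor upgrade seriousness or causality of a reported AE. It does not provide for adding one.
- Protocol 14.2 has a general review for accuracy and completeness, with queries. It names no check of AEs against acuity.
- SAP 6.5.10 lists losses of two lines or more. The listing does not feed the rate.

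None does.

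**6. Size, by illustration only.** The plan states no figure for this rate. The nearest is in SAP section 7: with 360 subjects and a true rate of 1.0%, the chance of seeing at least one event is at least 97%. It reproduces: 1 − 0.99^360 = 97.3% (and 1 − 0.9917^360 = 95.0% at 0.83%). That figure assumes every event is captured. With capture share s it becomes 1 − (1 − 0.01s)^360, which is 96.1%, 93.3% and 83.5% at s = 90%, 75% and 50%.

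For 450 eyes, true rate r and capture s, expected uncounted eyes are 450 × r × (1 − s). The chance of at least one is 1 − (1 − r(1 − s))^450. Both r and s are assumptions.

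| r | s = 90% | s = 75% | s = 50% |
|---|---|---|---|
| 0.5% | 0.23 eyes; 20% | 0.56; 43% | 1.13; 68% |
| 1% | 0.45; 36% | 1.13; 68% | 2.25; 90% |
| 2% | 0.90; 59% | 2.25; 90% | 4.50; 99% |

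These lean high. An eye already counted for another sight-threatening event is not lost from the composite, and with up to 20% attrition assumed, some of the 450 eyes will have no exit acuity.

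**The case against.** The endpoint is a rate of adverse events, all six components come from the AE form, and an AE source for an AE rate is coherent. The event is pre-listed, must be reported as an SAE, and falls under sponsor data review. Protocol 14.2 also calls for a data validation plan before the first subject's first visit. That plan is not among the documents and may already contain a check of AE entries against acuity. The loss would not be hidden either, since a 15-letter drop would normally appear in the 2-line outcome and in the listing.

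Much of this stands. The documents do not permit non-reporting, and the chance of a miss is reduced. What does not follow is that the rate is complete. Neither document states a derivation or reconciliation, and visibility in a listing is not inclusion in the numerator. The AE source also has real value: SAP section 3 drops unscheduled-visit data from summary tables except for AEs.

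A reader might also infer that the 2-line and 3-line tables will contradict each other. In general they will not. The 2-line outcomes can be met at any postoperative visit, with each subject counted once, whereas the 3-line loss must be present at exit, so an eye in one and not the other is often correct. The true conflict is confined to an eye that is three or more lines down at exit with no item b) entry. Nor does the open-label design add much in a single-arm study.

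**Conclusion.** The point holds as a gap in the SAP's data-source specification. A component defined by acuity values is taken solely from AE item b), although the values that decide it are collected and are used for the milder outcomes. Any omission would be a reporting failure under the protocol, and no stated step corrects it in the rate.

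Its reach is limited. The rate is descriptive. The primary endpoint, its exact test, the type I error, the power and the sample size do not depend on it. A reader might want to attach a number of percentage points to the undercount, but the documents give neither a true 3-line rate nor a capture share, so its size cannot be estimated. The table above shows only what assumed values would imply. The conclusion itself rests on the text of SAP 6.3 and Appendix C and on the absence of a stated cross-check. If the unseen validation plan contains one, the practical risk is smaller still, but the SAP should say so.

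**What to change.** In SAP Appendix C, derive the component from Visual Acuity_VAS and Visual Acuity_VAS_1: BCDVA at Visit 8 or early exit at least 15 letters below the best BCDVA in the study. State whether the best may be the screening reading (with or without the brightness acuity test) or the Visit 1 pinhole reading, because that choice changes which eyes qualify.

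Keep item b) as a supplementary source, for example where exit acuity is missing or the loss was seen at an unscheduled visit. Before database lock, list and query every eye where the derived result and item b) disagree. A tick contradicted by the acuity data is then resolved rather than counted automatically, and a derived loss with no entry is sent back to the site as a possible unreported SAE.

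The cost is SAP wording, slight extra programming on data already collected, some queries, and a rate that may rise slightly.
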